# 5.2.2 Secondary Endpoints

The secondary endpoints for this study are as follows:

- Mean change in fat fraction of vastus lateralis and soleus comparing Magnetic Resonance Spectroscopy (MRS) before and after 12 months of treatment with givinostat versus placebo.
- Mean change in fat fraction of pelvic girdle and lower limb muscles comparing Magnetic Resonance Imaging (MRI) before and after 12 months of treatment with givinostat versus placebo.
- Mean change in Cross Sectional Area (CSA) of pelvic girdle and lower limb muscles comparing MRI before and after 12 months of treatment with givinostat versus placebo.
- Mean change in other histology parameters (e.g. CSA, MFAF, regenerative fibers) comparing the histology biopsies before and after 12 months of treatment with givinostat.
- Mean change in Motor Function Measurement (MFM) before and after 12 months of treatment with givinostat versus placebo.
- Mean change in Time Function Tests (time to climb four standard steps, time to rise from floor and time to walk/run 10 m) before and after 12 months of treatment with givinostat versus placebo
- Mean change in 6 Minute Walking Test (6MWT) before and after 12 months of treatment with givinostat versus placebo.
- Proportion of patients with < 10% worsening in 6MWT at the end of study.

- Proportion of patients who lose the ability to rise from floor (Baseline through end of study).
- Proportion of patients who lose ambulation during the study.

17 June 2020 Page 41 of 110

- Mean change in muscle strength evaluated by knee extension, elbow flexion as measured by Hand Held Myometry (HHM), before and after 12 months of treatment with givinostat versus placebo.
- Mean changes in quality of life (assessed by the 36-item Short Form survey [SF36]) before and after 12 months of treatment with givinostat as compared to placebo.

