4.4.2. Handling of Missing Data/Imputation/Censoring Rules

For the primary efficacy endpoint, defined as mean fibrosis % from baseline to 12 months of therapy, as well as for the key secondary endpoint (MRI) different multiple imputation approaches will be applied to handling missing data. Further details on the missing imputation strategies are provided in Section 6.3.1 of the present document for the primary efficacy endpoints, and in Section 6.3.2.2 and 6.3.2.3 for the key secondary endpoints.

Results for the other efficacy and safety endpoints will be based on non-missing data only (i.e. missing observations will not be replaced).

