6.3.2.5. Time function test (TFT)

Definition

Time Function Tests (TFT) evaluation will include:

- Time to climb four standard steps (4-Stair Climb)
- Time to rise from floor
- Time to walk/run 10m

Analysis methodology

The absolute value of time to 4-Stair Climb and change versus baseline, at each time point, will be summarized as a continuous variable using descriptive statistics. A box-

Sponsor: ITALFARMACO
Protocol: DSC/15/2357/53

plot of the average time to 4-Stair Climb at each visit will also be produced by treatment group.

To make best use of repeated intra-subject evaluations of 4-Stair Climb, the absolute change in time to 4-Stair Climb from baseline to visits 8, 9 10 and 11 (months 3, 6, 9 and 12) will analyzed as described for MFM using an MMRM analysis. Fixed effect class terms will be included for treatment, visit, visit x treatment interaction and concomitant steroid use at baseline; baseline value will be included as a covariate. An unstructured covariance matrix will be used to model the within-subject error. LSmeans and SEs and also the difference in LSmeans between treatments will be extracted by visit; SEs, 2-sided 95% CIs and 2-sided p-values will also be extracted for the difference in LSmeans. The principal focus of inference will be the results at visit 11 (month 12).

Possible need for log transformation of this variable will be assessed by check of ANCOVA model residuals. If considered non-Normal, a supportive analysis will be performed on the log scale.

The same analyses will be done for time to rise from floor and time to walk/run 10 m. A box-plot of the average time to rise from floor and time to walk/run 10 m at each visit will also be produced by treatment group.

Number of patients who declined to perform the test or didn't complete it (e.g. for Rise From Floor and 10-Metre Walk/Run Test) will also be provided.

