Finally, the proportion of patients who lose the ability to rise from floor during the study (defined as patients with Rise From Floor grading = 0) will be summarized at each time point after baseline as a discrete variable using descriptive statistics. The rising from floor grading will also be summarized as discrete variable, at each time point, using descriptive statistics. The proportion of patients who lose ability to rise from floor after 12 months of therapy will be also compared between arms using a stratified Cochran Mantel-Haenszel (CMH) chi square test with a two-sided α =0.05 level. The stratification factor is concomitant steroid use at baseline. The proportion, along with its exact two-sided 95% CI, will be computed within each treatment group. A two-sided 95% CI for difference of proportion between the treatment groups will also be computed. Patients where there are missing data such that retention or loss of the ability to rise from floor cannot be determined will be included in the analysis as having lost the ability to rise from floor.

Data handling rules

In case of patients with no TFT assessments, as the MMRM approach implicitly imputes missing data as missing at random, there will be no separate analysis imputing missing values, the analysis will be based on the observed data at visits 8, 9 10 and 11.

Sponsor: ITALFARMACO
Protocol: DSC/15/2357/53

6.3.2.6. 6-Minute Walking Test (6MWT)

Definition

6 Minute Walking Test (6MWT) evaluation will include:

- Distance walked after 6 minutes
- Proportions of patients with <10% worsening in the distance walked after 6 minutes
- Proportions of patients who lose ambulation during the study

For patients who do not complete the test, the max distance walked will be considered as distance walked after 6 minutes.

For patients who were not able to do the test, due to lack of ambulation, "zero" will be imputed as maximum distance walked.

The average of the distance at screening and randomization will be used as baseline value.

Analysis methodology

The absolute value of the maximum distance walked and change versus baseline, at each time point, by treatment group will be summarized as a continuous variable using descriptive statistics. A box-plot of the average maximum distance walked at each visit will be produced by treatment group.

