6.3.3. Exploratory efficacy analysis

Evaluation of LTBP4 and osteopontin genotype

In order to determine whether the effects of givinostat versus placebo are related to the type of Mutation Exon or the LTBP4 and Osteopontin (i.e. SPP1) genotypes, three further subgroups of subjects will be defined: Mutation Exon (Exon 45, Prior to exon 45, Post-exon 45), LTBP4 (IAMM, VTTT, Other, VTTT+Other) and SPP1 (TT, GT, GG, GG+GT).

The number and proportion of patients in each subgroup will be summarized as appropriate. Further analyses are described in Section 6.5.

Evaluation of the functional test velocity

Velocity for each functional test will be computed at each visit from the following variables:

- 4-Stair ascent duration
- Rising from floor duration
- 10-Metre Walk/Run test duration

For patients with missing data TFT data due to lack of ability to perform the test, their velocity will be set equal to zero.

Velocity to 4-Stair Climb will be calculated according to the following formulas:

$$Velocity_{4-Stair\ Climb} = \frac{4}{time\ to\ climb\ 4\ stair}$$

Sponsor: ITALFARMACO
Protocol: DSC/15/2357/53

The velocity will be set to zero for patients who don't attempt the test with reason "Unable to physically perform the test" or for patients with the lowest grade (1) for the 4 Stair Climb test.

The absolute value of velocity to 4-Stair Climb and change versus baseline, at each time point, will be summarized as continuous variables using descriptive statistics.

To make best use of repeated intra-subject evaluations of 4-Stair Climb velocity, the absolute change from baseline to visits 8, 9 10 and 11 (months 3, 6, 9 and 12) will be analyzed using mixed model repeated measures (MMRM) analysis. Fixed effect class terms will be included for treatment, visit, visit x treatment interaction and concomitant steroid use at baseline; baseline value will be included as a covariate. An unstructured covariance matrix will be used to model the within-subject error. LSmeans and SEs and also the difference in LSmeans between treatments will be extracted by visit; SEs, 2-sided 95% CIs and 2-sided p-values will also be extracted for the difference in LSmeans. The principal focus of inference will be the results at visit 11 (month 12).

Velocity to walk/run 10 m will be calculated according to the following formula:

$$Velocity_{walk/run \ 10 \ m} = \frac{10}{time \ to \ walk/run \ 10 \ m}$$

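### The secondary analysis of timed-test seconds treats a time that is absent because the patient cannot do the test as missing at random; inability is scored only in an exploratory velocity analysis

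*SAP*

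**What the plan says.** Protocol 5.2.2 lists mean change in the timed tests (4-stair climb, rise from floor, 10 m walk/run) as a secondary endpoint. Protocol 13.6.2 gives no rule for a patient who cannot do a test. SAP 6.3.2.5 analyses change in seconds at Visits 8 to 11 by MMRM, with inference centred on Visit 11. Its data-handling rule reads "In case of patients with no TFT assessments, as the MMRM approach implicitly imputes missing data as missing at random"; it rules out any separate imputation and adds that "the analysis will be based on the observed data at visits 8, 9 10 and 11". SAP 4.4.2 sets the general rule for endpoints other than the primary and key secondary: "Results for the other efficacy and safety endpoints will be based on non-missing data only (i.e. missing observations will not be replaced".

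Three other places in the SAP deal with inability differently:

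- SAP 6.3.3 (exploratory): "For patients with missing data TFT data due to lack of ability to perform the test, their velocity will be set equal to zero".
- SAP 6.3.2.5, responder endpoint for rise from floor (secondary, stratified CMH test): "Patients where there are missing data such that retention or loss of the ability to rise from floor cannot be determined will be included" as having lost it.
- SAP 6.3.2.6 (secondary, 6MWT distance): "For patients who were not able to do the test, due to lack of ambulation", zero is imputed.

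**The concern.** SAP 6.3.3 shows that inability leaves a missing time. That time is absent because function fell below what can be timed, so its absence is itself the outcome. Under missing at random the model fills the gap with the time expected from the patient's earlier visits and from patients still able. For someone who cannot do the test, that time does not exist.

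The timed tests serve the objective of slowing disease progression. If one arm loses more patients to inability, its fitter patients carry the Visit 11 comparison, and it can look as stable as the other arm. Fibrosis, MRI and histology each have a missing-not-at-random sensitivity analysis (SAP 6.3.1, 6.3.2.2, 6.3.2.3). The timed tests have none.

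**Working it through.** **Step 1: how each test handles inability at secondary level.**

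| Test | MMRM of seconds (SAP 6.3.2.5) | Secondary responder endpoint | Velocity zero (SAP 6.3.3) |
|---|---|---|---|
| 4-stair climb | missing at random | none | exploratory only |
| Rise from floor | missing at random | yes, loss of ability (CMH) | exploratory only |
| 10 m walk/run | missing at random | partly, through loss of ambulation (CMH, SAP 6.3.2.6) | exploratory only |

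The 4-stair climb has the largest gap.

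**Step 2: who leaves the model.** The response is change from baseline, and baseline is also a covariate.

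- Unable at baseline: no covariate and no change score, so not in the model. Protocol 7.1 requires 200 to 450 m on the 6MWT but no ability to rise or climb, so such patients can enter.
- Unable from Visit 8 on: a baseline but no response, so no contribution.
- Able at first, unable by Visit 11: earlier visits count, and Visit 11 is in effect predicted from them.

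**Step 3: arithmetic for abrupt loss.** The plan states no figure to reproduce. Arm sizes of 34 and 17 come from SAP 3.5; everything else here is assumed. Suppose f of 17 placebo patients and no givinostat patients lose the ability, everyone else slows by 1 s, those lost had baseline time b, and inability is scored at 30 s. Differences are givinostat minus placebo.

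- Observed times only: 1 - 1 = 0 s.
- Inability scored: 1 - [(17 - f) x 1 + f x (30 - b)]/17.
- f = 3, b = 15: 1 - (14 + 45)/17 = -2.47 s.
- f = 3, b = 10: 1 - (14 + 60)/17 = -3.35 s.
- f = 3, b = 20: 1 - (14 + 30)/17 = -1.59 s.
- f = 1, b = 15: 1 - (16 + 15)/17 = -0.82 s.

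**Step 4: simulation.** 34 v 17 patients, four visits, 3000 runs per scenario, median baseline 8 s. The observed-time column uses sequential regression on earlier visits, a close stand-in for the MMRM. The other two columns are month-12 ANCOVAs, with inability scored as 30 s or as velocity 0. Loss rates, drift and the 30 s cap are assumptions.

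| Pattern | Loss, placebo v givinostat | Observed times, MAR | Scored at 30 s | Velocity 0 (per s) |
|---|---|---|---|---|
| Abrupt, months 9 to 12 | 5% v 5% | 0.0 s | 0.0 s | 0.000 |
| Abrupt | 12% v 6% | 0.0 s | -1.0 s | +0.006 |
| Abrupt | 18% v 6% | 0.0 s | -2.1 s | +0.012 |
| Abrupt | 24% v 6% | 0.0 s | -3.2 s | +0.018 |
| Abrupt | 6% v 18% | 0.0 s | +2.1 s | -0.012 |
| Abrupt | 6% v 24% | 0.0 s | +3.3 s | -0.019 |
| Gradual, visible slowing | 8% v 5% | -1.2 s | -1.2 s | +0.010 |
| Gradual | 12% v 5% | -2.5 s | -2.5 s | +0.021 |
| Gradual | 17% v 4% | -4.2 s | -4.0 s | +0.031 |
| Gradual | 22% v 8% | -4.8 s | -4.2 s | +0.031 |

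In the abrupt rows both arms drift by the same 1 s a year, so loss of ability is the only difference, and the observed-time analysis cannot see it. In the gradual rows the slowing shows in earlier times and the model recovers it. It slightly exceeds the scored value at the higher loss rates, where the score is held at the 30 s cap.

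**The case against.** The strongest reply is that the plan already shows loss of function at secondary level. Rise from floor has a stratified CMH comparison, with undeterminable status counted as lost, and its grading is tabulated by visit. Loss of ambulation has a CMH comparison too. SAP 6.3.2.5 also reports how many patients declined or did not complete a test. This stands for rise from floor and in part for the 10 m test. It does not help the 4-stair climb, and counts of non-completers are descriptive only.

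Second, the zero-scored velocity MMRM is already specified for all three tests, is returned to the seconds scale, and is the measure used for the timed-test subgroups in SAP 6.5. With no alpha adjustment and no testing hierarchy, raising its level changes prominence and not an error rate. That is true, and it is also why the change is cheap. Prominence still matters: as written, the secondary result for these tests is the one that leaves inability out.

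Third, the size rests on assumptions. Protocol 4.1 describes Becker progression as slower and more variable than Duchenne, and four post-baseline visits give the model a chance to see decline before loss. This stands as a limit on how large the bias is likely to be. It does not make the rule right for loss that is abrupt or occurs before Visit 8.

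A reader might also infer that the SAP contradicts itself by scoring the same inability as zero in the 6MWT. It does not. That zero is for lack of ambulation, and a patient who cannot climb or rise may still walk a measured distance. Zero metres is also a real distance, whereas no finite time stands for inability. The 6MWT rule is a parallel in principle only.

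**Conclusion.** The concern holds for the secondary analysis of seconds, most fully for the 4-stair climb, least for rise from floor. The rule treats informative absence as missing at random and drops patients with no baseline or no post-baseline time.

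The documents give no rate of loss, so the size cannot be fixed. Under the assumed scenarios the observed-time result is within about 0.6 s of the scored result when slowing is seen first. When loss is abrupt it misses the whole difference, 1 to 3 s for a gap in loss rates of 6 to 18 percentage points, whichever arm loses more.

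Two stronger readings are tempting and not supported. One is that the plan ignores loss of function at secondary level; the two responder endpoints show otherwise. The other is that the analysis is known to be biased for or against givinostat; neither direction nor size can be derived from the documents. The primary endpoint and sample size are not affected.

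**What to change.** Before unblinding, state in SAP 1.1 and 6.3.2.5 that the velocity MMRM of SAP 6.3.3 is reported at secondary level for all three tests. Velocity is 0 when the recorded reason is physical inability or the grade is the lowest; declined and other reasons stay missing. Draw inference on the velocity scale, because the reciprocal of a mean velocity is not a mean time. Keep the MMRM of seconds, as the protocol's endpoint, labelled as conditional on being able to do the test.

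At minimum, add a prespecified sensitivity analysis of times that ranks inability as the worst outcome.

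The cost is SAP wording and no new data. The velocity method is already specified, though the documents do not show that it is programmed. The downsides are less familiar units, a departure from the protocol's time endpoint that must be documented, and floor values from patients unable at baseline, who cannot worsen on this scale.

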6.3.2.7. Hand Held Myometry (HMM)

Definition

Muscle strength measured by Hand Held Myometry (HHM) evaluation will include:

Sponsor: ITALFARMACO
Protocol: DSC/15/2357/53

- left knee extension measurements
- right knee extension measurements
- left elbow flexion measurements
- right elbow flexion measurements

For these variables the highest values among the three measurements at each evaluation will be considered for the present analysis.

Analysis methodology

The absolute value of right/left knee extension and change versus baseline, at each time point, will be summarized as a continuous variable using descriptive statistics.

The absolute change in right/left knee extension from baseline to visits 8, 9 10 and 11 (months 3, 6, 9 and 12) will be calculated as the difference between the mean of right/left knee extension measurements at each visit and baseline. These data will be analyzed using mixed model repeated measures (MMRM) analysis. Fixed effect class terms will be included for treatment, visit, visit x treatment interaction and concomitant steroid use at baseline; baseline value will be included as a covariate. An unstructured covariance matrix will be used to model the within-subject error. LSmeans and SEs and also the difference in LSmeans between treatments will be extracted by visit; SEs, 2-sided 95% CIs and 2-sided p-values will also be extracted for the difference in LSmeans. The principal focus of inference will be the results at visit 11 (month 12).

Possible need for log transformation of this variable will be assessed by check of ANCOVA model residuals. If considered non-Normal, a supportive analysis will be performed on the log scale.

The same analyses will be done for right/left elbow flexion.

Data handling rules

As the MMRM approach implicitly imputes missing data as missing at random, there will be no separate analysis imputing missing values, the analysis will be based on the observed data at visits 8, 9 10 and 11.

6.3.2.8. Quality of Life (SF-36)

Definition

SF-36 will include:

- Single items
- 8 Domains
- Total Score

Sponsor: ITALFARMACO Protocol: DSC/15/2357/53

SF-36 questionnaires will be analysed using PRO CoRE software.

Analysis methodology

Summary descriptive statistics will be provided at each time point by treatment group for the quality of life scores/domains as assessed by the SF-36 questionnaire.

Data handling rules

The PRO CoRE Software applies a value to a scale item rendered missing if at least one of the items in that scale has valid data. A scale receives a "missing" score (".") only if all the items in that scale are missing. Physical Component Summary (PCS) and Mental Component Summary (MCS) are calculated when at least seven of the eight profile scales have valid data, either actual or estimated.

However, to calculate PCS, the Physical Functioning (PF) scale must be one of the seven scales having valid data. Also, to calculate MCS, the Mental Health scale must be one of the seven scales having valid data.

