# 5.1.2 Secondary Objectives

The secondary objectives of this study are the following:

- To establish the macroscopic muscle effects of givinostat versus placebo administered chronically over 12 months assessed by MRI/MRS.
- To establish the other histological effects of givinostat versus placebo administered over 12 months.
- To establish the efficacy of givinostat versus placebo administered chronically over 12 months in slowing disease progression.
- To assess the safety and tolerability of givinostat versus placebo administered chronically.
- To evaluate the pharmacokinetic (PK) profile of givinostat administered chronically in the target population.
- To evaluate the impact of givinostat versus placebo administered chronically on quality of life and activities of daily living.

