6MWT=6-minute walking test; AE=adverse event; MFM= Motor Function measure; SF36= Short Form (36) Health Survey; PT=Prothrombin time; aPPT= activated partial thromboplastin time; ECG= electrocardiogram; ECHO= echocardiogram; PK= pharmacokinetics; MRI= magnetic resonance imaging; FEV1= forced expiratory volume at 1 second; FVC=forced vital capacity; PEF= peak expiratory flow; RBC-red blood cell; WBC=white blood cell; ALT=alanine aminotransferase; AST=aspartate aminotransferase; LDH= lactate dehydrogenase; CRP=C-reactive protein; GGT=gamma-glutamyl transpeptidase; BUN=blood urea nitrogen; fT3= free T3 (the active part of triiodothyronine); fT4=Free T4 (the active part of thyroxine); TSH=thyroid-stimulating hormone; eGFR=estimate Glomerular Filtration Rate; HHM=hand-held myometry; MMT=manual muscle testing

- \* Unscheduled visits may take place at the discretion of the Investigator such as additional cardiology visits at the study center or visits at the patient's home by a qualified trained nurse for blood sample collection.
- If the patient is discontinued from the study treatment, the patient will be asked to return for the early withdrawal visit to be performed within 4 weeks
  of the last dose of study treatment. In this case, the SF-36 evaluation and MRI may not be performed.
- The patients who complete the study (i.e. 12 months of treatment) will be asked to return to the centre for the Follow-up visit to be performed after 4
  weeks from the last dose of study treatment (i.e. 4 weeks ±1).
- 3. A 12-lead ECG is to be done in triplicate at the screening visit and during the other visits if an ECG demonstrates a prolonged QTcF interval > 450 msec obtained on 2 more ECGs over a brief period. The averaged QTcF values of the 3 ECGs is to be used to determine whether the patients should be discontinued from the study.
- Pulmonary function tests: FEV1, FVC and PEF.
- Serology CMV IgM, HBsAg/HCV/HIV, EBV IgG.

17 June 2020 Page 61 of 110

- 6. Hematology test: RBC, WBC (including differential count), hemoglobin, MCH, MCHC, MCV, hematocrit, and platelets. Test will be done according to the schedule (i.e., every two weeks the first 2 months of treatment) and are to be performed more frequently if clinically indicated. Note: Repeat visits for the platelets count will be performed at the request of the Investigator.

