## 9.1.1 Visit 1 and Visit 2 - Screening (Week -4 + 2 weeks)

The Screening visits (Visit 1 and Visit 2) will occur within 4 weeks (± 2 weeks) prior to the Randomization Visit. The following assessments will be performed at Visit 1:

- Written Informed Consent
- Eligibility criteria: review of inclusion and exclusion criteria
- Medical history and demographic data
- Prior medications (taken in the past 6 months)
- Physical examination
- Vital signs (blood pressure, heart rate and body temperature)
- Weight and height
- 12-lead ECG (in triplicate)
- Echocardiogram
- Pulmonary function tests: FEV1, FVC, FEV1/FVC, and PEF
- Blood collection for:
  - serology
  - hematology
  - blood chemistry
  - coagulation tests (prothrombin time [PT] and activated partial thromboplastin time [aPTT])
  - thyroid function tests (TSH, fT3, fT4)
- Urine analysis
- Quality of Life test (SF-36)
- 6MWT + MFM
- Muscle strength test (knee extension and elbow flexion by HHM)
- Time function tests
- AE assessments

17 June 2020 Page 63 of 110

If all inclusion and exclusion criteria have been met and the patient is eligible, an MRI, MRS and muscle biopsy are to be performed before the first IMP dose. At the discretion of the Investigator, patients not meeting inclusion/exclusion criteria may be re-screened twice with an interval of at least 30 days between assessments.

At Visit 1, after having filled in the "Eligibility criteria" section of the eCRF, eligible patients will be randomized to one of the two following muscle biopsy sequences by the system:

V2: Right Arm - V11: Left Arm

V2: Left Arm - V11: Right Arm

The site will receive the muscle biopsy sequence by email.

Randomization will be balanced in a ratio of 1:1 and will not be stratified.

If needed for logistic reasons, Visit 2 can be completed on two different days included in the window period between Visit 1 and Visit 3. Patients will be instructed to avoid physical activity that would exceed their normal activity for 3 days before each visit.

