The proportion of patients who lose ambulation during the study, as assessed by 6MWT, will be compared between arms using a stratified Cochran Mantel-Haenszel (CMH) chi square test with a two-sided α=0.05 level. As for the primary endpoint, the stratification factor is concomitant steroid use at baseline. The proportion, along with its exact two-sided 95% CI, will be computed within each treatment group. A two-sided 95% CI for difference of proportion between the treatment groups will also be computed. In case of patients with no 6MWT assessment at 12 months/EOS, the last available score will be used for the analysis

 Change in muscle strength evaluated by knee extension and elbow flexion after 12 months of therapy

The absolute change in muscle strength evaluated by knee extension and elbow flexion after 12 months of therapy, as assessed by HHM, will be analyzed using an ANCOVA model similar to the one described for the primary endpoint. Possible need for log transformation of this variable will be assessed by check of ANCOVA model residuals.

Change in quality of life after 12 months of therapy

Summary descriptive statistics will be provided at each time point for the quality of life scores/domains as assessed by the SF-36 questionnaire.

17 June 2020 Page 90 of 110

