To evaluate the impact of givinostat versus placebo administered chronically on quality of life and activities of daily living.	Quality of life test (SF-36): 1- Items 2- Domains: 1- Physical Functioning (PF) 2- Role-Physical (RP) 3- Bodily Pain (BP) 4- General Health (GH) 5- Vitality (VT) 6- Social Functioning (SF) 7- Role-Emotional (RE) 8- Mental Health (MH) 9- Total score	Mean changes in quality of life (SF-36) before and after 12 months of treatment with givinostat as compared to placebo.
	Adverse events	

ODUCCTIVES	VADIABLES	ENDROINTS
OBJECTIVES	VARIABLES	ENDPOINTS
To assess the safety and tolerability of givinostat versus placebo administered chronically.	Vital Signs: 1- Height 2- Weight 3- Body mass index (BMI) 4- Sitting blood pressure systolic 5- Sitting blood pressure diastolic 6- Heart rate 7- Temperature	Number and proportion of patients experiencing treatment-emergent adverse events (TEAEs) and serious adverse events (SAEs) from Baseline through end of study (EOS). Summary of type, incidence, and severity of TEAEs and SAEs (Baseline through EOS). Changes from baseline to end of study of vital signs.
	Laboratory tests: 1- Biochemistry 2- Hematology 3- Coagulation 4- Urinalysis	Changes from baseline to end of study of clinical laboratory tests.
	Physical examination	Changes from baseline to end of study of physical examination.
	Pulmonary function:	
	 Forced Vital Capacity (FVC) Forced Expiratory - Volume at 1 second (FEV1) FVC/FEV1 Peak Expiratory Flow (PEF) 	Changes from baseline to end of study of pulmonary function.
	Cardiac function parameters	

ODIFOTUES	MADIANIES	ENDROUNTS
OBJECTIVES	VARIABLES	ENDPOINTS
	1- ECG 2- ECHO	Changes from baseline to end of study of Cardiac function parameters.
To evaluate the pharmacokinetic (PK) profile of givinostat administered chronically in the target population	Details will be provided in a specific PK protocol.	Summary of the PK of givinostat and its major metabolites.
Secondary Exploratory objective(s):	Exploratory variable(s):	Exploratory endpoint(s):
To evaluate the correlation between the PK profile of givinostat and pharmacodynamics (PD) data.	Details will be provided in a specific Statistical Analysis Plan.	PK-PD correlation analyses between metrics of exposure and the efficacy/safety endpoints of givinostat.

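### SF-36 is defined as a 12-month change versus placebo, but the planned analysis stops at scores by time point, so the plan does not estimate its own endpoint

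*SAP*

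**What the plan says.** **Objective.** Protocol 5.1.2 lists as a secondary objective: "To evaluate the impact of givinostat versus placebo administered chronically on quality of life and activities of daily living".

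**Endpoint.** Protocol 5.2.2 defines it as the mean SF-36 change "before and after 12 months of treatment with givinostat as compared to placebo". SAP section 2 repeats this: "Mean changes in quality of life (SF-36) before and after 12 months of treatment with givinostat as compared to placebo".

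**Analysis.** Protocol 13.6.2 places the item under a title about change in quality of life, but the text beneath it reads: "Summary descriptive statistics will be provided at each time point for the quality of life scores/domains as assessed by the SF-36 questionnaire". SAP 6.3.2.8 adds only the split by arm: "Summary descriptive statistics will be provided at each time point by treatment group for the quality of life scores/domains".

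**Schedule.** Table 5 and Protocol 9.1.1 and 9.1.10 place SF-36 at Visit 1 and at Visit 11 (Week 48), with no assessment in between. On early withdrawal, Table 5 footnote 1 says: "In this case, the SF-36 evaluation and MRI may not be performed". Section 9.1.10 likewise does not require it at that visit.

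**Missing data.** SAP 4.4.2 leaves missing values unreplaced for endpoints other than the primary and key secondary ones. The software rule in SAP 6.3.2.8 completes scales with missing items; it does not supply a questionnaire that was never filled in.

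**The concern.** A secondary endpoint worded as a change relative to placebo needs, at the least, a change and a contrast between the arms. Neither is planned. The other continuous efficacy measures have both: MRS, MRI and the main histology parameters get a change analysed by ANCOVA, and MFM, timed tests, 6MWT and myometry get a change analysed by MMRM.

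Two things are at stake. First, with about 17 placebo patients, a raw Week-48 comparison carries chance baseline imbalance into the result and comes with no stated uncertainty. Second, if no contrast or lead score is fixed in advance, any comparison made later can be picked from single items, eight domains, a total score, PCS and MCS after the results are known.

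The optional questionnaire at early withdrawal is a lesser matter. Protocol 7.3 stresses that data from the final evaluation matter because withdrawal may be linked to the drug's safety. The visit text nevertheless makes the questionnaire optional, while the waiver does not extend to the muscle biopsy.

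**Working it through.** **1. Does any other text supply the contrast?** SAP 1.1 says that other secondary endpoints move from ANCOVA to MMRM. This does not reach SF-36: Protocol 13.6.2 never gave SF-36 an ANCOVA, only one post-baseline assessment is scheduled, and the specific section (6.3.2.8) remains descriptive.

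**2. Can the reader recover the endpoint from the planned tables?** Only roughly. Subtracting the mean at Visit 1 from the mean at Visit 11 compares different sets of patients once any Week-48 form is missing. The uncertainty cannot be recovered, because with equal SDs at both visits the SD of the change is SD × √(2(1 − r)), and r, the within-patient correlation, is not reported. It is 1.00 SD at r = 0.5 and 0.77 SD at r = 0.7 (both values of r assumed).

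**3. Sample size available.** The documents give no SF-36 figure. Their own calculation is for total fibrosis (difference 9, SD 10, two-sided 5%, 2:1). It reproduces: 30:15 gives 79.4% power and 32:16 gives 82.1%, so 48 is the smallest 2:1 total reaching 80%; 48/0.95 = 50.5, rounded up to 51 (34:17). It says nothing about power for SF-36 and is used here only for the arm sizes.

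**4. Precision if a contrast is added.** No SF-36 SD or target difference is given, so results are in SD units. Half-width = t(0.975, n1 + n2 − 2) × √(1/n1 + 1/n2).

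For 34:17: √(1/34 + 1/17) = 0.297; t(49) = 2.01; half-width = 0.60 SD.

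| SF-36 available (assumed) | 95% CI half-width | Difference with 80% power | Power for an assumed 0.5 SD |
|---|---|---|---|
| 34:17 (51) | 0.60 SD | 0.85 SD | 38% |
| 31:15 (46) | 0.63 SD | 0.90 SD | 34% |
| 27:14 (41) | 0.67 SD | 0.95 SD | 32% |

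The lower rows represent roughly 10% and 20% missing. These rates are assumptions.

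**5. Gain from adjusting for baseline.** The half-width is multiplied by √(1 − r²). At r = 0.5: 0.60 × 0.866 = 0.52 SD. At r = 0.7: 0.60 × 0.714 = 0.43 SD. If the scale had an SD of 10 points (assumed), the unadjusted and the two adjusted half-widths would be about 6.0, 5.2 and 4.3 points.

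**The case against.** The best defence is that description was intended. The synopsis, Protocol 13.6.2 and the SAP all treat SF-36 this way. The safety objective is also phrased as givinostat versus placebo, and safety is summarised without a formal contrast. Total fibre counts, which sit under a secondary endpoint, are descriptive as well. With power of about 38% for half an SD, a formal analysis would settle little and would add comparisons to a plan with no multiplicity control.

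Part of this stands. Precision is low and the result can only be supportive. But the SF-36 endpoint is itself defined as a change compared with placebo, and even the fibre counts get a change-from-baseline summary. Consistent description does not make the analysis match the endpoint, and low precision is a reason to show an interval.

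Four stronger readings are tempting, and the documents do not support them:

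- *The trial cannot answer the question.* It can. SF-36 is scheduled at baseline and Week 48 in both randomised arms; what is missing is the analysis.
- *SF-36 is skipped at early withdrawal.* Both places make it optional; neither forbids it.
- *The omission favours givinostat.* Severe drug-related diarrhoea and drug-related SAEs are among the grounds for permanent discontinuation (Protocol 7.3.1), so missingness could be related to treatment. But no rate, arm split or reasons for SF-36 missingness are given, and the withdrawal visit may fall up to four weeks after the last dose. The direction is unknown.
- *Daily living is left without a measure.* SAP section 2 assigns the combined objective to SF-36, including the Physical Functioning and Role-Physical domains.

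**Conclusion.** The point holds as a mismatch between endpoint and analysis. The plan as written does not estimate a stated secondary endpoint, although the data needed are scheduled in both arms. It touches neither the primary endpoint nor the sample size, but it goes beyond missing detail because no text elsewhere supplies the contrast.

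An added contrast would have a 95% CI half-width of about 0.6 SD at 34 versus 17, rising to about 0.67 SD if a fifth of the forms are missing and falling to about 0.43–0.52 SD with baseline adjustment. These figures rest on the planned arm sizes, the assumed missingness and the assumed correlations of 0.5 to 0.7. The early-withdrawal waiver is a secondary weakness: it may lose data, possibly for treatment-related reasons, but neither the amount nor the direction can be sized from the documents.

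**What to change.** **Main change, in SAP 6.3.2.8, before unblinding.** Add the change in SF-36 from baseline to Visit 11. Analyse it with the ANCOVA of SAP 6.3.2.1 and 6.3.2.2: baseline score as covariate, treatment and baseline steroid use as class terms. Report the adjusted difference with its 95% CI. Name the scores in advance, for example PCS and MCS, which the section's software rules already cover, with the eight domains as supportive. State that the results are supportive and not adjusted for multiplicity. If the sponsor prefers description only, the objective and endpoint should be reworded to say so.

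**Secondary change, in Protocol Table 5 footnote 1 and 9.1.10.** Ask for SF-36 at the early-withdrawal visit for patients still on study. Report those scores separately or in a sensitivity analysis, and do not enter them as Week-48 values.

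**Cost.** The main change is SAP wording and one more use of an existing model, at the price of a few more unadjusted comparisons with wide intervals. The secondary change needs a protocol amendment (Protocol 14.6.1) and a few minutes per withdrawing patient. SAP 3.5 reports enrolment complete, so it cannot recover forms already missed; most of the value lies in the SAP change.
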